8.2.4 Statistical Methods

Safety (All Parts)

Incidence of adverse experiences will be descriptively summarized. Summary statistics and plots will be generated for the change from baseline values in the vital signs, ECG parameters, and selected laboratory safety parameters for subjects, as deemed clinically appropriate. Depending on the safety parameter, the difference from baseline will either be computed on the original scale (raw change from baseline) or on the log scale and back- transformed for reporting (percent change from baseline). Summary statistics for the raw laboratory safety tests, ECGs, and/or vital signs may also be computed, as deemed clinically appropriate.

Pharmacodynamics

Part I

The whole body and internal organ radiation burden associated with a single IV dose of [¹¹C]MK-6884 (~ 370 MBq, \leq 4.9 μ g) administered to healthy subjects will be estimated using methods from the site. The primary measure of radiation safety will be the Effective Dose (ED), a weighted composite measure of the radiation absorbed doses in multiple compartments.

Part II

Brain extraction and grey and white matter segmentation will be performed in each subject's MRI scan. A human brain atlas will be aligned to the extracted subject MRI brain via a non-linear registration algorithm.

[¹¹C]MK-6884 dynamic PET images will be corrected for decay, scatter, random coincidences, photon attenuation and motion (frame to frame registration). The test PET scan will be aligned to the extracted subject MRI brain via a rigid registration algorithm. The aligned brain atlas will then be applied to the motion corrected PET dynamic data to generate time activity curves (TACs) of several brain regions, including (but not limited to) striatum, cortex, and cerebellum. The retest PET scan will be coregistered to the first scan and TACs will be generated using the previously defined ROIs for that subject.

At least the following analyses will be used for [¹¹C]MK-6884 binding quantification (index of M4 PAM receptor availability) in human brain from both test and retest scans:

- a) Regional volumes of distribution (V_T) will be estimated by means of compartmental modeling and an arterial input function which represent the parent concentration of [¹¹C]MK-6884 in plasma. A one or two tissue compartment model will be selected on the basis of a model selection metric (e.g. AIC). Additional tests such as V_T time stability will also be performed to guide the selection of an appropriate scanning time and to support the development of simplified quantification techniques such as standardized uptake value ratios.
- b) Non-displaceable binding potential (BP_{ND}) will be estimated for target M4 receptor rich region(s) based on tissue-ratio (transient equilibrium) method, as well as simplified reference tissue model (SRTM), with a suitable reference region that is devoid of M4 receptors. Based on preclinical studies in NHP PET and human brain autoradiography study, striatum (putamen and caudate) and cerebellum has been identified as the M4 receptor rich and poor regions, respectively. To validate the accuracy/bias in measurements, the BP_{ND} derived from both tissue-ratio method and SRTM will be compared to that derived from volumes of distribution. i.e.
$$\frac{V_T^{\text{target}}}{V_T^{\text{reference}}} - 1$$
- c) Standardized uptake value ratio (SUV_R) will also be evaluated as part of the development of a simplified quantification strategy for [¹¹C]MK-6884. Standardized uptake value (SUV) represent the activity in the brain (or brain region) obtained during an specific time window normalized by total injected activity and whole body weight. SUV_R is a semi-quantitative measure of specific tracer uptake using a reference region which accounts for the non-displaceable signal present in the target region(s) (e.g. striatum).

$$SUV_R = \frac{SUV_{t_1, t_2}^{\text{target}}}{SUV_{t_1, t_2}^{\text{reference}}}$$

where $SUV_{t_1, t_2}^{\text{target}}$ and $SUV_{t_1, t_2}^{\text{reference}}$ are the standardized uptake values of the target and reference regions respectively between the times t_1 and t_2 . SUV_R can be a surrogate for V_T or BP_{ND} where in static rather than dynamic scans are sufficient for quantifying M4 receptor availability. However, SUV_R can be of limited use as the data from reference region may be noisy because of low tracer uptake.

The test-retest variability (expressed in percentage) of the M4 receptor availability index (V_T or BP_{ND} or SUV_R) will be calculated by

$$T/RT \text{ variability} = 2 \frac{|Index^{\text{test}} - Index^{\text{re-test}}|}{Index^{\text{test}} + Index^{\text{re-test}}} \times 100$$

Less than 10% T-RT variability is ideal and less than 20% T-RT variability on average is acceptable for a PET tracer

d) If needed, additional methods may also be employed, to more robustly characterize the tracer kinetics in both healthy and AD subjects

Part III

Brain extraction and grey and white matter segmentation will be performed in each subject's MRI scan. A human brain atlas will be aligned to the extracted subject MRI brain via a non-linear registration algorithm.

[¹¹C]MK-6884 dynamic PET images will be corrected for decay, scatter, random coincidences, photon attenuation and motion (frame to frame registration). The PET scan will be aligned to the extracted subject MRI brain via a rigid registration algorithm. The aligned brain atlas will then be applied to the motion corrected PET dynamic data to generate time activity curves (TACs) of several brain regions, including (but not limited to) striatum, cortex, and cerebellum.

As AD subjects will undergo PET scans without arterial input function, the analyses that will be used for [¹¹C]MK-6884 binding quantification (index of M4 PAM receptor availability) in brain include BP_{ND} and/or SUV_R and will be determined as described in Part II. These parameters will be determined on an individual as well as on average basis.

Blood samples for AChE plasma concentration and RBC-AChE activity will be measured prior to [¹¹C]MK-6884 dosing. The information on plasma concentration and RBC-AChE activity will be used to explore quantitative relationships between BP_{ND} vs. plasma concentration and BP_{ND} vs. RBC-AChE activity using regression analysis or non-linear mixed effect modeling. The measured plasma concentration and RBC-AChE activity will

also be compared to pharmacokinetic/pharmacodynamics relationships described in the scientific literature, which may facilitate further analysis of the data.

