Part II will begin the process of validating and qualifying [¹¹C]MK-6884 as a M4 PAM tracer in humans. The parameter of interest to be quantified from the PET baseline scans will be nondisplaceable binding potential (BP_{ND}) or distribution volume (V_T), an index of receptor availability. If needed, additional methods may also be employed, to more robustly characterize the tracer kinetics in both healthy and AD subjects. The possibility of reliably quantifying M4 receptor availability will be determined by measurement of the intra-subject baseline test-retest [T-RT] variability or within-subject coefficient of variation. A baseline magnetic resonance imaging (MRI) scan of the brain will be obtained for region-of-interest (ROI) delineation. Subjects will be administered 2 separate single IV doses of approximately 370 MBq (10 mCi, ≤ 4.9 µg) [¹¹C]MK-6884 with a brain PET/CT scan performed after each dose. PET images of the brain will be obtained for up to approximately 90 minutes after each administration of [¹¹C]MK-6884. There will be a wash-out of at least 3 hours between each drug administration to allow for most of the radioactivity from the first scan to decay prior to starting the second scan. In case of technical difficulties, the duration between the two scans may be adjusted at the investigator's discretion. A minimum of 6 subjects will be tested in Part II. Up to 4 additional subjects may be tested if unexpected levels of variability are observed in the first 6 subjects of Part II.

Part III

In parallel with Part II, Part III will begin the process of validating and qualifying [¹¹C]MK-6884 as a M4 PAM PET tracer in AD patients based on the results of Part I and in comparison to an age matched population of healthy elderly subjects in Part II (i.e., the AD patients enrolled in Part III will be in the same age range [55 to 85 years of age, inclusive] as

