8.2.1 Hypotheses

Part I

Primary

1. Dosimetry calculations based on Part 1 data will support multiple [¹¹C]MK-6884 injections in humans.

Part II

Primary

1. The average intra-subject T-RT variability of M4 receptor density index measured from [¹¹C]MK-6884 PET data is acceptable ($\leq 20\%$).

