8.2.2 Analysis Endpoints

Primary (Safety)

Safety and tolerability will be assessed throughout the study by monitoring subjects for clinical adverse experiences. Physical examinations, vital signs, 12-lead electrocardiograms (ECG) and laboratory safety tests will be performed periodically to detect any medically meaningful effects of the tracer on physiology.

Primary (Pharmacodynamics)

Whole body and internal organ radiation dose will be evaluated by whole body PET scans (Part I). Efficacy measurements to investigate M4 PAM receptor availability and its inter-subject variability in healthy subjects (Part II) will be evaluated via two administrations of [¹¹C]MK-6884 and brain PET scanning and will include: (1) volume of distribution, or one of its surrogate (2) test-retest variability of volume of distribution, or one of its surrogate. Efficacy measurements to investigate M4 PAM receptor availability and its inter-subject

variability in AD patients (Part III) will be evaluated via single administration of [¹¹C]MK-6884 and brain PET scanning and will include: (1) binding potential, or one of its surrogate.

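### The Part II 20% test-retest limit names no index or region, and the three indices it covers are not equally hard to pass

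*Combined protocol and SAP*

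**What the plan says.** Section 8.2.1 (and 3.1) sets the limit on "The average intra-subject T-RT variability of M4 receptor density index measured from" the tracer's PET data: at most 20%. No index, estimator or region is given.

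Other sections describe the index differently:

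- Section 2.1, Part II: "The parameter of interest to be quantified from the PET baseline scans will be nondisplaceable binding potential" or V_T. SUVR is not listed.
- Section 4.2.3.1: V_T, BP_ND and/or SUVR.
- Section 8.2.2: "test-retest variability of volume of distribution, or one of its surrogate".
- Section 8.2.4, Part II: "The test-retest variability (expressed in percentage) of the M4 receptor availability index (V_T or BP_{ND} or SUV_R) will be calculated by" a single formula, followed by the statement that "less than 20% T-RT variability on average is acceptable for a PET tracer".

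Section 8.2.4 also opens its list of methods with "At least the following analyses will be used for" binding quantification on both scans, so V_T, BP_ND and SUVR are all planned outputs. BP_ND has two reference-region estimators, and the BP_ND "derived from both tissue-ratio method and SRTM will be compared to that derived from volumes of distribution". On SUVR it says that "SUV_R can be a surrogate for V_T or BP_{ND} where in static rather than dynamic scans are sufficient", and adds a caution about noise in the reference region. Striatum is called receptor rich and cerebellum receptor poor, but the 20% limit is attached to neither. Section 8.2.5 says that one hypothesis will be formally evaluated; it does not choose an index.

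**The concern.** An acceptance limit needs one quantity to act on. Here three quantities share a formula and a limit, yet they contain different amounts of non-displaceable signal. That signal enlarges the denominator of the T-RT formula without enlarging the difference in the numerator, so an index that includes it can look more reproducible than the specific-binding measure from the same scans.

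At stake is the meaning of the Part II conclusion. Part III has no arterial input and reports BP_ND and/or SUVR as in Part II, and its exploratory regressions use BP_ND. A statement that the tracer met 20%, if based on SUVR or V_T, would not show that BP_ND is reproducible to 20%.

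**Working it through.** **Inputs.** The T-RT formula and the 20% limit come from 8.2.4, and N = 6 to 10 from 8.2.6. The 20% is a fixed criterion and 8.2.6 reports no sample size calculation, so the plan has no derived figure to reproduce. The documents give no human BP_ND and no noise level; both are assumed below and shown as ranges.

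**1. SUVR against BP_ND.** Let a and b be test and retest BP_ND, with mean BP, and take SUVR as 1 + BP_ND.

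- T-RT(BP_ND) = 200|a − b| / (a + b) = 200|a − b| / (2BP)
- T-RT(SUVR) = 200|a − b| / (a + b + 2) = 200|a − b| / (2(1 + BP))
- So T-RT(SUVR) = T-RT(BP_ND) × BP/(1 + BP)

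Setting SUVR at 20% gives BP_ND T-RT = 20(1 + BP)/BP, which is 40.0%, 30.0% and 26.7% at BP 1, 2 and 3.

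Example: SUVR 2.15 and 1.85 gives 200 × 0.30/4.00 = 15% (meets the limit). Minus 1, the pair is 1.15 and 0.85, giving 200 × 0.30/2.00 = 30% (does not). While SUVR exceeds 1 the reverse cannot happen.

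The identity does not cover BP_ND from the simplified reference tissue model (SRTM).

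**2. How often this changes the answer.** Simulation of 400,000 trials: signed percentage differences on BP_ND normal, with mean absolute value equal to the true T-RT; equal BP in all subjects; SUVR computed from the same differences. Percentage of trials with average T-RT of at most 20%, N = 6:

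| True BP_ND T-RT | On BP_ND | On SUVR, BP 1 | On SUVR, BP 2 | On SUVR, BP 3 |
|---|---|---|---|---|
| 10% | 99.8 | 100 | 100 | 100 |
| 15% | 85.8 | 100 | 99.8 | 98.8 |
| 20% | 52.7 | 99.8 | 93.6 | 85.7 |
| 25% | 27.5 | 96.4 | 75.4 | 61.2 |
| 30% | 13.7 | 85.8 | 52.6 | 38.3 |

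At N = 10 and a true value of 25%, the figures are 20.7 on BP_ND against 98.9, 80.3 and 62.8 on SUVR. A 20% between-subject CV in BP moves the N = 6 figures by under 1 point (checked at 15% and 25%).

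A second simulation used a different error model: lognormal SUVR with 10% between-subject SD on the log scale, N = 6. With 10% within-subject SD, SUVR met the limit and BP_ND did not in 62%, 26% and 13% of trials at mean SUVR 2, 3 and 4. With 5% within-subject SD this fell to 2%, 0% and 0%.

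**3. V_T against BP_ND.** From the V_T ratio minus 1 expression in 8.2.4, target V_T = reference V_T × (1 + BP). To first order, with independent normal reference-region variation r and BP_ND T-RT t:

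T-RT(V_T) = √[(t × BP/(1 + BP))² + r²]

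At t = 25% and BP = 2 this gives 16.7%, 17.4%, 19.4% and 22.4% for assumed r of 0, 5, 10 and 15%. The matching N = 6 pass rates are 75, 70, 56 and 39%, against 27% on BP_ND. V_T T-RT reaches the BP_ND value only when r² = 25² − 16.7², that is r of about 18.6%. So V_T is also easier to pass over most of this range, but less predictably than SUVR.

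**The case against.** The case against giving this much weight is strong, and most of it stands.

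- A reader might infer that the sponsor could declare success on SUVR and leave a failing BP_ND out of sight. The documents do not support that. Section 2.1 limits the parameter of interest to BP_ND or V_T. Section 8.2.4 makes SUVR's role as a surrogate conditional and warns of its limits. All three indices are to be computed on both scans, and 8.2 requires changes to the analysis plan to be listed and explained in the study report.
- A reader might also infer that a lenient pass would release Part III. It would not: under 2.1, Part III starts once at least three Part II subjects have completed, in parallel with Part II.
- Determining an index of receptor availability is itself a Part II objective (3.1), and the V_T model and BP_ND methods are to be compared on the data. Fixing every detail in advance would pre-empt that. This limits what the fix should prescribe: the documents do not favour SRTM over the tissue ratio, and give no figure for how closely the two must agree with V_T.
- Arterial sampling may stop after the first three subjects (2.1; 6.1.2, footnote r), which might suggest a verdict on V_T from three subjects. Section 4.2.3.1 speaks of at least six for T-RT, so that reading is not intended, although the N behind each index may differ.
- Human BP_ND and noise are unknown, and with a very reproducible tracer every index passes.

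What remains is that no section says which index decides. The caution in 8.2.4 about SUVR concerns reference-region noise; it does not address the denominator effect or remove SUVR from the limit.

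**Conclusion.** The point holds in a limited form. The 20% limit is attached to no index or region, and V_T, BP_ND and SUVR give different answers under it from the same scans. For SUVR against SUVR minus 1 the direction is fixed, and 20% on SUVR is 40%, 30% or 27% on BP_ND at BP_ND 1, 2 or 3. At a true BP_ND T-RT of 25% and N = 6, the limit is met in about 27% of trials on BP_ND and in 96, 75 or 61% on SUVR. At a true value of 10% the choice makes no practical difference.

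These sizes rest on assumed BP_ND and error distributions, and on reading tissue-ratio BP_ND as SUVR minus 1 with matching window and regions. The missing assignment of the limit rests on none of them. It affects how the Part II conclusion is worded, not access to data or any decision inside this protocol. Severity: minor.

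**What to change.** In 8.2.1 and 8.2.4, before any T-RT value is computed:

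- Tie the 20% conclusion to the average T-RT of striatal BP_ND with the cerebellar reference. This matches the plan's own use of BP_ND in 2.1 and in the Part III regressions.
- Use one BP_ND estimator, chosen on the accuracy comparison with V_T-derived BP_ND already planned in 8.2.4, and not on T-RT results.
- Do not apply the 20% limit to raw SUVR. Compute any tissue-ratio T-RT on SUVR minus 1.
- Report V_T, SUVR and other regions descriptively, each with its N.
- If the reference region is not supported, report striatal V_T T-RT labelled as V_T, and state that it does not show BP_ND to be reproducible to 20%. As step 3 of the working shows, V_T at the same limit is not an equivalent substitute.

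Cost: wording only, with no new scans or samples. The headline figure may look less favourable than SUVR would have, and the estimator choice must be documented before T-RT is computed.

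Separately, 2.1 treats the reference region as something this trial can validate, while 4.2.3.1 says that studies outside this protocol are needed. Those two statements should be reconciled.

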8.2.5 Multiplicity

No multiplicity adjustment is needed. Only one of the hypotheses will be formally evaluated.

8.2.6 Power

Up to 26 (N=3-6 in Part I, N=6-10 in Part II, and N=7-10 in Part III) subjects will be included in the study. Given the investigational nature of this study no sample size calculation has been performed.

9.0 LABELING, PACKAGING, STORAGE AND RETURN OF CLINICAL SUPPLIES

9.1 Investigational Product

The investigator shall take responsibility for and shall take all steps to maintain appropriate records and ensure appropriate supply, storage, handling, distribution and usage of investigational product in accordance with the protocol and any applicable laws and regulations.

Table 9 Product Descriptions

Product Name & Potency	Dosage Form
[¹¹ C]MK-6884 370 MBq (10 mCi) containing ≤4.9 µg MK-6884	A sterile solution

All other supplies not indicated in [Table 9](#) above will be provided centrally by the Sponsor or locally by the trial site, subsidiary or designee, depending on local country operational or regulatory requirements.

For any commercially available product that is provided by the trial site, subsidiary or designee every attempt will be made to source these supplies from a single lot/batch number. The trial site will be responsible for recording the lot number, manufacturer and expiry date of any locally purchased product.

9.2 Packaging and Labeling Information

Clinical supplies will be affixed with a clinical label in accordance with regulatory requirements.

9.2.1 Supply of Precursor and Synthesis/Labeling of [¹¹C]MK-6884

Merck Research Laboratories (MRL) will supply the local radiochemistry synthesis laboratory with the radiopharmaceutical precursor to MK-6884. [¹¹C]MK-6884 will be generated from the precursor compound after a final synthetic step.

MRL will also supply a nonradioactive version of MK-6884 to be used as an analytical standard during quality control procedures, and a Certificate of Analysis describing the precursor as well as the nonradioactive standard, will be provided.

Radiolabeling and sterile solution compounding will be conducted under the appropriate cGMP standards for clinical PET materials at this stage of development. The final compounded product will be in a sterile solution containing up to 10% (v/v) ethanol, 10 mM sodium phosphate buffer, pH 7 in 0.9% sodium chloride for injection. The radiopharmaceutical formulation will be prepared shortly before administration by the local radiochemistry synthesis laboratory. Unit doses that pass quality control procedures for radiochemical purity will be dispensed to physicians in the PET unit, using standard operating procedures for the production, transfer, and administration of radiopharmaceuticals.

A qualified staff member who is authorized to administer unsealed radioactive material to human beings may inject the radiopharmaceutical formulation intravenously after confirming that the batch passed all necessary quality control procedures and verifying that the radiation dose is correct.

9.3 Clinical Supplies Disclosure

This trial is open-label; therefore, the subject, the trial site personnel, the Sponsor and/or designee are not blinded. Treatment (name, strength or potency) is included in the label text; random code/disclosure envelopes or lists are not provided.

9.4 Storage and Handling Requirements

Clinical supplies must be stored in a secure, limited-access location under the storage conditions specified on the label.

Receipt and dispensing of trial medication must be recorded by an authorized person at the trial site.

Clinical supplies may not be used for any purpose other than that stated in the protocol.

9.5 Discard/Destruction>Returns and Reconciliation

The investigator is responsible for keeping accurate records of the clinical supplies received from the Sponsor or designee, the amount dispensed to and returned by the subjects and the amount remaining at the conclusion of the trial. For all trial sites, the local country Sponsor personnel or designee will provide appropriate documentation that must be completed for drug accountability and return, or local discard and destruction if appropriate. Where local discard and destruction is appropriate, the investigator is responsible for ensuring that a local discard/destruction procedure is documented.

10.0 ADMINISTRATIVE AND REGULATORY DETAILS

10.1 Confidentiality

10.1.1 Confidentiality of Data

By signing this protocol, the investigator affirms to the Sponsor that information furnished to the investigator by the Sponsor will be maintained in confidence, and such information will be divulged to the institutional review board, ethics review committee (IRB/ERC) or similar or expert committee; affiliated institution and employees, only under an appropriate understanding of confidentiality with such board or committee, affiliated institution and employees. Data generated by this trial will be considered confidential by the investigator, except to the extent that it is included in a publication as provided in the Publications section of this protocol.

